#### 8.1.1.5 Patient Diary

During the allergy season, patients will receive a daily diary with a series of numeric questions to be answered electronically for measurement of the daily symptom and daily medication score, including use of a rescue inhaler for patients with asthma. Patients will be considered compliance if they complete at least 50% of expected daily responses. Patients will receive reminders from the EDC system via text message or email, as well as general outreach from TASC regarding their AIT journey.

#### 8.1.1.6 End-of-Study Visit

At the conclusion of the 2018-2019 Mountain Cedar pollen season, TASC will contact study subjects to schedule and end-of-study visit. At this visit, the following procedures will be performed:

- Assess patient for any changes to medical history, including adverse events since the previous visit, resolution of ongoing adverse events from Visit 3, or changes in concomitant medication use
- Physical exam
- Order allergen specific serum IgE testing
- Collect vital signs
- Assess patient for any changes to medical history, adverse events since the previous visit, or changes in concomitant medication use
- Administer patient-reported outcomes, including treatment satisfaction
- Complete entry of patient information into the EDC system (eCRF)

## 8.2 SAFETY AND OTHER ASSESSMENTS

The following procedures will be performed as part of the safety and other assessment of the patient during this study:

- **Physical examination** including height and weight, body systems review
- **Vital signs** including temperature, pulse, respirations, and blood pressure
- **Special assays or procedures** include a Urine Pregnancy Test (UPT) for women of childbearing potential. As noted in Section 2, the risk of AIT during pregnancy is low, but immune sensitivity reactions and use of histamine in diagnostic allergy testing can be associated with pre-term delivery.

- **Administration of questionnaires** for patient-reported outcomes, including the NRS-11 for injection site pain, and treatment satisfaction.
- **Assessment of adverse events.** AEs/SAEs will be collected spontaneously and using the Total Safety Score (TSS) a structured worksheet for collecting and evaluating expected adverse events of interest (AEIs) associated with AIT.

In the event that a subject experiences either:

1. A treatment-emergent, serious adverse event that is related to study treatment, or
2. A grade 3 systemic allergic reaction according to WAO criteria, as assessed on the TSS worksheet that is possibly or definitely related to study treatment, or
3. Any other treatment-emergent adverse event resulting in death

The study will be placed on hold to further evaluate the risks and benefits of the study before a decision is made on whether or not to continue or terminate the study.

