### 8.3.8 EVENTS OF SPECIAL INTEREST

Adverse Events of Interest (AEIs) include symptoms associated with local and systemic allergic reactions to AIT, up to and including anaphylaxis. Such events will be evaluated on the TSS worksheet rather than reported on separate AE or SAE forms. Specific AEIs associated with AIT include: Confusion, hypotension/collapse, unconsciousness, bradycardia, pallor, and urinary or fecal incontinence, which will be used to define severe reactions on the TSS worksheet. Diaphoresis, vomiting, presyncope, dyspnea, stridor, wheeze, chest/throat tightness or laryngeal edema, nausea, vomiting, and abdominal pain will define moderate reactions and reactions limited to the skin, including urticaria, erythema, injection site pruritis and angioedema will be defined as mild.

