**14 APPENDIX 3 ASSESSMENT TOOLS AND RATING SCALES**

**Total Safety Score (TSS) Worksheet**

Subject ID:

Injection # (write in 1, 2, or 3):

RECORDING INSTRUCTIONS: Mark/code the box(es) indicating reactions experienced by this subject following injection (D = definitely related to study, P = probably related to study, N = not related to study)

ILIT protocol defined grading scale for severity# of adverse events			
	Mild	Moderate	Severe
LOCAL REACTIONS			
Lymph node swelling			
Itch			
Redness			
Other*			
SYSTEMIC REACTIONS			
Rhinorrhea			
Sneezing			
Dyspnea			
Cough			
Wheeze			
Pruritus			
Rash			
Angioedema			
Nausea			
Vomiting			
Diarrhea			
Headache			
Other*			

SCORING INSTUCTIONS: Give one score for most severe reaction (see scoring key on back) - min score 0, max score 4

SCORE for this injection	
---------------------------------	--

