**Total Safety Score Scoring Guide**

Safety Scoring Key	
Reaction	Point value
None	0
Local - if any marks in white boxes	1
Systemic mild (WAO Grade 1/2) - if any marks in green boxes	2
Systemic moderate (WAO Grade 3) - if any marks in yellow boxes	3
Systemic severe (WAO Grade 4) - if any marks in red boxes	4

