10. SAFETY ANALYSIS

Safety analyses will compare treatment groups using appropriate methods according to their nominal or quantitative nature and will include descriptive statistics rather than formal hypothesis testing for noninferiority due to the small overall sample size. The study included a formal stopping rule in the event two systemic allergic reactions were detected.

The total safety score (TSS) and proportion of subjects with any treatment-emergent SAE, as defined in the composite safety endpoint, will be assessed using the Mann-Whitney test. Data will be presented in the form of descriptive statistics and appropriate tables and graphs with a conclusion on whether the significance level allowed the null hypothesis for each test to be rejected.

Safety Objective: To evaluate the safety profile of ILIT versus placebo using a standardized scoring system, the Total Safety Score worksheet, for AEs of interest (AEIs) up to 60 minutes post-procedure.

Statistical Analysis Plan

Safety Endpoints:

- Proportion of subjects experiencing a serious, treatment-emergent AE up to 60 minutes after an intranodal injection procedure
- Proportion of subjects experiencing systemic reactions to ILIT relative to placebo and severity of reactions relative to placebo as assessed by the Total Safety Score (TSS)
- Proportion of subjects reporting local injection site reactions relative to placebo and severity of local reactions relative to placebo, as assessed by the TSS

Additional safety tables and listings will include summaries of all patients experiencing anaphylaxis or treated with epinephrine, by group and a table of TSS reactions by severity by group.

Safety Population:

Safety analysis will include all participants who received at least one dose of study intervention regardless of whether they provided any diary data.

Calculation cumulative safety score (sum of TSS) across all patients by group will be performed in accordance with the scoring instruction described in section 7.4

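### The study-hold rule uses a grade and relatedness terms that do not match the worksheet it relies on, and the SAP describes a different rule

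*Protocol*

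**What the plan says.** Protocol 8.2 lists three events, any one of which, in one subject, places the study on hold while risks and benefits are reviewed:

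1. An SAE that emerges on treatment and is judged related to it.
2. "A grade 3 systemic allergic reaction according to WAO criteria, as assessed on the TSS worksheet that is possibly or definitely related"; the relation meant is to the injections under study.
3. A death from any further adverse event that emerges on treatment.

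The second trigger points to the TSS worksheet in Appendix 3. The worksheet's relatedness codes are "D = definitely related to study, P = probably related to study, N = not related to study". Its scoring guide has a level above grade 3, "Systemic severe (WAO Grade 4) - if any marks in red boxes", and the footnote maps moderate to WAO grade 3 and severe to grades 4/5. For adverse events in general, Protocol 8.3.3.2 uses a two-way scale, Related or Not Related.

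Protocol 8.3.8 says of allergic reactions, up to and including anaphylaxis: "Such events will be evaluated on the TSS worksheet rather than reported on separate AE or SAE forms". Protocol 8.3.3.1 likewise says that events captured on the worksheet are not reported separately as adverse events. Protocol 8.3.2 makes seriousness a matter of the sponsor-investigator's view.

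SAP 10 states: "The study included a formal stopping rule in the event two systemic allergic reactions were detected".

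**The concern.** A hold rule has to be applied on the day, from what the form records. Here the form and the rule use different vocabularies, and the rule names one grade on a scale that goes higher. The SAP then reports a rule with a different count and different qualifying events.

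Protocol 2.2 describes this as the first trial of intralymphatic treatment for mountain cedar allergy. No interim analysis is planned (Protocol 9.4.6). Safety oversight lies with the sponsor-investigator and a sub-investigator, who also treat participants (Protocol 10.1.6). Protocol 8.2 holds the only hold rule in the protocol that is defined by specific events, so its wording carries weight. The report is also at stake: if written from the SAP, it would describe a stopping rule that the protocol does not contain.

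**Working it through.** The documents give no operating characteristic for either rule, so there is no figure to reproduce. The check is a comparison of texts.

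**Grade.** Trigger 2 names grade 3, with no word on higher grades. The worksheet scores grade 3 as 3 points and grade 4 as 4 points.

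**Relatedness.** Three vocabularies are in use:

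- Trigger 2: possibly, definitely.
- Worksheet: definitely, probably, not.
- Protocol 8.3.3.2: Related, Not Related.

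*Possibly* is on neither recording scale, and *probably* is not in the rule.

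**Route for higher grades.** A related reaction judged life-threatening is an SAE under Protocol 8.3.2 and meets trigger 1. A fatal one meets trigger 1 or 3. The judgement of seriousness belongs to the sponsor-investigator. The worksheet as reproduced records severity and relatedness but has no field for seriousness.

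**The two rules applied to the same events**, read literally:

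| Event | Protocol 8.2 | SAP 10 |
|---|---|---|
| One grade 3 reaction, not serious, coded definitely | Hold (trigger 2) | Not met |
| One grade 3 reaction, not serious, coded probably | Not literally covered | Not met |
| One related grade 4/5 reaction, judged serious | Hold (trigger 1) | Not met |
| One related, non-fatal grade 4 reaction, not judged serious | Not literally covered | Not met |
| Two mild (grade 1/2) reactions, not serious | Not met | Met; no grade is stated |

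The rules diverge in both directions, so neither is uniformly stricter.

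**Effect of the count alone (illustration).** Take n = 16 active patients, from the ceiling of 16 per group in Protocol 9.2. Let p be the chance that a patient has a qualifying event, assumed equal under both rules. Take the two SAP reactions to be in two patients.

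- P(at least 1) = 1 − (1 − p)^16
- P(at least 2) = 1 − (1 − p)^16 − 16p(1 − p)^15

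| p | At least 1 | At least 2 |
|---|---|---|
| 1% (anaphylaxis rate quoted in Protocol 3) | 14.9% | 1.1% |
| 5% (assumed) | 56.0% | 18.9% |
| 10% (assumed) | 81.5% | 48.5% |
| 20% (assumed) | 97.2% | 85.9% |

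In practice p would differ between the rules, because they count different events. The table isolates the change from one event to two.

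**The case against.** The best defence is that Protocol 8.2 works if read as a whole. Trigger 1 applies when a subject experiences a related SAE, whichever form is used, and 8.2 itself says that SAEs are also collected through the TSS. The composite safety objective in Protocol 3 lists anaphylaxis and epinephrine use ahead of any other SAE, which implies that these count as serious; Protocol 9.4.4 treats the composite in the same way. On relatedness, *probably* is ordinarily stronger than *possibly*, so a sensible investigator would count a reaction coded as probably related.

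Much of this stands. A reader might infer that a grade 4 reaction escapes the hold, and the documents do not support that. A related severe reaction would usually reach trigger 1, and a fatal one trigger 1 or 3. The residual gap is a reaction above grade 3 that is not judged serious. A reader might also infer that 8.2 is the only protection available. It is not: Protocol 10.1.2 allows suspension for unacceptable risk or by decision of the principal investigator or sponsor-investigator, and Protocol 7.1 lets the investigator stop an individual's treatment at any time.

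On the SAP, the defence is that its sentence looks back. SAP 6.2 was written after all patients had been enrolled, and SAP 1 gives the SAP precedence for analytic purposes only. That is fair: the sentence does not displace 8.2 as the rule for conduct. It remains a misdescription. SAP 1 promises that discrepancies with the protocol will be described, and this one is not.

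The defence does not remove the mismatch in the text. It relies on the reader supplying grades and relatedness terms that the rule does not contain.

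**Conclusion.** The rule is wrong as written, as an internal inconsistency, and should be corrected. Three points hold:

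- Trigger 2 does not name grades above 3, and its relatedness terms fit neither recording scale. A grade 3 reaction coded as probably related is not literally covered.
- Cover for grade 4/5 reactions comes through the SAE and death triggers. For a non-fatal reaction it depends on a seriousness judgement, while 8.3.3.1 and 8.3.8 keep these reactions off AE and SAE forms.
- SAP 10 describes a different rule. It calls for two reactions where the protocol needs one event, sets no grade or relatedness condition, has no SAE or death limb, and is called a stopping rule where the protocol has a hold pending review.

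There are two rules here, not more: the differing relatedness scales are a fault within the protocol rule. A reader might take the SAP to mean reactions of any grade, but it states no grade either way. The result for two mild reactions rests on reading that silence as no restriction.

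The size is best seen in the event comparison. On the count alone, under the equal-rate assumption with 16 patients, the chance of meeting the trigger is 14.9% against 1.1% at a 1% rate and 97.2% against 85.9% at 20%. Nothing here shows that a hold was missed.

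**What to change.** Reconcile Protocol 8.2, 8.3.3.1, 8.3.3.2, 8.3.8, the Appendix 3 worksheet and scoring guide, and SAP 10, so that one hold rule appears throughout. State its grade range, the number of events and the relatedness categories in terms that the worksheet can record. Say how a worksheet reaction is assessed for seriousness, so that the route to trigger 1 is explicit.

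Correct the SAP sentence to describe the rule that actually governed conduct. Since the SAP postdates enrolment, the report should state which rule was applied and disclose the discrepancy.

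Which rule applies is for the sponsor and IRB to decide; this review takes no position on it. The cost is a protocol clarification and one SAP sentence, with no change to sample size or to the efficacy analysis.

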## 8.3 ADVERSE EVENTS AND SERIOUS ADVERSE EVENTS

### 8.3.1 DEFINITION OF ADVERSE EVENTS (AE)

Any untoward medical occurrence in a clinical investigation subject administered immunotherapy or matched placebo which does not necessarily have a causal relationship with the treatment and is not otherwise related to their underlying medical condition or a comorbid condition present at the time of enrollment. An AE can therefore be any unfavorable and unintended sign, symptom, or disease temporally associated with the use of the immunotherapy or other medicinal product, whether or not related to the medicinal product, that has an onset after enrollment in the study and the initiation of treatment, defined as the injection of study treatment and the seven day period following. Events reported via the patient diary on the daily symptom score are by definition symptoms of the underlying disease and are therefore not adverse events. Symptoms may fluctuate and thus changes in symptoms are not considered adverse events but are rather measures of treatment efficacy for the underlying condition. Pre-planned procedures are not considered adverse events. Pre-existing conditions, unless worsened are not considered adverse events. Whenever possible, adverse events will be consolidated into the underlying diagnosis rather than a collection of separately reported symptoms, as determined by the investigator.

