## 8.3.4 TIME PERIOD AND FREQUENCY FOR EVENT ASSESSMENT AND FOLLOW-UP

The occurrence of an adverse event (AE) or serious adverse event (SAE) may come to the attention of study personnel during study visits and interviews, or other contacts with a study participant during the treatment and follow-up period.

All AEs will be captured on the appropriate case report form (CRF). Information to be collected includes event description, date of onset, clinician’s assessment of severity, relationship to study product as assessed by the investigator, and date of resolution/stabilization of the event. All AEs occurring while on study must be documented appropriately, according to the definitions in Section 8, regardless of

relationship. All AEs will be followed to adequate resolution or the end-of-the study. Local and systemic reactions during the 60-minute observation period will be captured on the Total Safety Score report form which includes specific criteria for assessing and grading adverse reactions to AIT. For patients experiencing a reaction, the observation period will be extended until the patient is stable. In accordance with Section 2.1, after each treatment visit, patients are counseled on how to recognize the signs of delayed-onset reactions, including worsening pain, tenderness, redness, swelling at the injection site and to assess the injection site for these symptoms for seven (7) following treatment. If they recognize these or other symptoms of a delayed-onset reaction, they are instructed to report these symptoms by phone.

Any medical condition that is present at the time that the participant is screened will be considered as baseline and not reported as an AE. However, if the study participant's pre-existing condition deteriorates at any time during the study, it will be recorded as an AE.

Changes in the severity of an AE will be documented to allow an assessment of the duration of the event at each level of severity to be performed. AEs characterized as intermittent require documentation of onset and duration of each episode.

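### Read literally, Protocol 8.3.1 and 8.3.8 allow a delayed asthma flare or allergic reaction to stay off the AE form, and hold trigger 2 in 8.2 reads the WAO grade only from the 60-minute worksheet

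*Protocol*

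**What the plan says.** **Protocol 8.3.1** makes four statements that bear on a flare of allergic disease after an injection:

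- Its first sentence defines an AE as an untoward occurrence that "is not otherwise related to their underlying medical condition or a comorbid condition present at the time of enrollment".
- Its second sentence takes in any unfavourable sign or symptom linked in time to treatment, whatever the cause, with onset from injection through the following seven days.
- After a sentence about the diary symptom score, it says that "changes in symptoms are not considered adverse events but are rather measures of treatment efficacy for the underlying condition".
- It then says: "Pre-existing conditions, unless worsened are not considered adverse events".

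**Protocol 8.3.4** says that if a participant's "pre-existing condition deteriorates at any time during the study, it will be recorded as an AE". It also says: "Local and systemic reactions during the 60-minute observation period will be captured on the Total Safety Score report form". Observation is extended only for patients who are already reacting. Patients are taught the signs of a delayed reaction, and "they are instructed to report these symptoms by phone". The section does not name the form on which such a call is recorded.

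**Protocol 8.3.8** says of local and systemic allergic reactions, up to anaphylaxis: "Such events will be evaluated on the TSS worksheet rather than reported on separate AE or SAE forms". It gives no time limit. On grading it says: "Diaphoresis, vomiting, presyncope, dyspnea, stridor, wheeze, chest/throat tightness or laryngeal edema, nausea, vomiting, and abdominal pain will define moderate reactions".

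**Protocol 8.2** puts the study on hold for a related, treatment-emergent SAE (trigger 1) or for a related WAO grade 3 systemic reaction as assessed on the TSS worksheet (trigger 2). Appendix 3 equates a moderate systemic reaction with WAO grade 3.

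**The SAP** lets its own definitions prevail for analysis (section 1) but does not define an AE. It scores the TSS at each treatment visit (7.4), states the TSS objective as up to 60 minutes (10), and summarises spontaneously reported AEs by counts and proportions (10.2).

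**The concern.** Patients with stable asthma are eligible, and Protocol 2.3.1 warns that systemic reactions can begin at any time after immunotherapy. The treatment itself could therefore provoke the comorbid or underlying disease. An AE definition that carves out anything related to that disease removes the events of most interest, and it conflicts with other rules in the same chapter without saying which prevails.

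The routing rule in 8.3.8 adds to this. Staff who apply it literally to a reaction at home would keep it off the AE and SAE forms, yet the worksheet it points to is completed during clinic observation.

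Two things are at stake. The first is whether such an event appears in the SAP 10.2 table. The second, and more important, is whether a delayed grade 3 reaction is seen by hold trigger 2, which takes its grade from that worksheet.

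**Working it through.** The plan gives no figure to reproduce, so the check sets the rules against one test case: wheeze at home on the evening after an injection, not serious, in a patient with stable asthma.

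| Provision | Effect on the test case |
|---|---|
| 8.3.1, first sentence | Not an AE if staff attribute it to the asthma |
| 8.3.1, second sentence | AE: linked in time, within seven days, cause irrelevant |
| 8.3.1, symptom-change sentence | Most naturally about diary symptoms; the six diary items are nasal and ocular and omit wheeze, but the sentence does not state that limit |
| 8.3.1, worsened conditions | AE |
| 8.3.4, deterioration rule | AE |
| 8.3.8, routing | TSS worksheet, not the AE or SAE form |
| 8.3.4 and SAP 10, TSS window | Outside the 60 minutes in which the worksheet is completed |
| 8.3.3.1 | Exempts from AE reporting only events captured on the TSS; this one was not captured |

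**Step 1, classification.** Three provisions make it an AE. One makes it a non-AE if read alone, and one is unclear. No text ranks them.

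**Step 2, form.** 8.3.8 points to the worksheet, while the TSS window and 8.3.3.1 point to the AE form. The second reading is the better one, but it has to be inferred.

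**Step 3, hold.** 8.3.8 grades wheeze as moderate, and Appendix 3 equates moderate with WAO grade 3, the level named in trigger 2. Trigger 2 sets no time limit but reads the grade from the TSS worksheet. The AE data items listed in 8.3.4 include severity but no WAO grade. The general severity scale in 8.3.3.1 is reserved for events outside the protocol grading system and the list of AEs of interest, and wheeze is on that list. The event therefore has no clear path to trigger 2 even if it is recorded as an AE.

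**Step 4, weight of one patient.** With 32 enrolled at 1:1 there are 32/2 = 16 per arm. With 23 enrolled the split is 12 and 11. A patient whose only AE is left off lowers that arm's AE proportion by 1/16 = 6.3 points, 1/12 = 8.3 points or 1/11 = 9.1 points. This is arithmetic per patient, not an estimate of bias, because the documents give no rate of delayed flares and no rate of misclassification.

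**The case against.** The strongest reply is that a careful reader would record the event. The second sentence of 8.3.1 covers it, 8.3.4 requires deterioration to be recorded, and 8.3.3.2 says the product must always be suspected and accepts a temporal relationship as enough for related. 8.3.3.1 reads as a rule against double reporting. The schedule of events lists AE review as a separate row from the TSS, including at the end-of-study visit, where no TSS is done. Investigators ask about AEs at each visit, and patients phone in delayed reactions. The SAP 10.2 table is descriptive, so no planned test depends on it.

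Most of this stands, and it rules out three stronger readings that a reader might infer:

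- **That delayed reactions go undetected or have nowhere to be recorded.** The phone instruction, the visit questions and the AE review row show otherwise. The gap is in classification and routing.
- **That serious delayed reactions would escape trigger 1.** 8.3.2 gives allergic bronchospasm treated in an emergency room or at home as an SAE example, and 8.3.4 covers serious, unexpected, related reactions until seven days after the third treatment.
- **That the probability of a lost event can be calculated.** Any assumed flare rate gives the chance that an event occurs, not that it is misclassified.

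The reply does not remove the literal conflict in 8.3.1, the missing time limit in 8.3.8, or the dependence of trigger 2 on one worksheet.

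**Conclusion.** The point holds as a defect in stated safety rules. Two provisions, followed as written, can keep a delayed asthma flare or allergic reaction off the AE form, and a non-serious delayed WAO grade 3 reaction would not clearly trip the study hold.

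Its reach is limited. The primary safety endpoint and the TSS scores are confined to 60 minutes and are unaffected, as is efficacy. SAP 10 summarises anaphylaxis and epinephrine use separately, so asthma flares and reactions short of anaphylaxis are the most exposed. Few events are expected, since Protocol 2.3.1 says few severe systemic reactions have been reported after sixty minutes. If extract provoked more delayed reactions than placebo, omissions would pull the descriptive AE comparison toward no difference, by an unknown amount.

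The conclusion assumes that some staff would apply the opening clause of 8.3.1 or the routing sentence of 8.3.8 literally. The documents neither show that this happened nor prevent it. It should be corrected because it bears on patient safety and costs little.

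**What to change.** 1. **Protocol 8.3.1:** delete the word *and* together with the clause "is not otherwise related to their underlying medical condition or a comorbid condition present at the time of enrollment". Limit the symptom exemption to nasal and eye symptoms scored in the diary.
2. **Protocol 8.3.8:** confine TSS-only recording to reactions that start within the observation period. Later reactions go on an AE or SAE form with a WAO grade.
3. **Protocol 8.2, trigger 2:** after the TSS worksheet, add *or the AE/SAE form* as a source of the grade.

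No extra rule making every worsening of rhinoconjunctivitis within seven days an AE is needed. Ordinary in-season symptoms remain diary outcomes.

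The cost is a few words of protocol text and one WAO-grade field on the AE form. Visit questions and phone reports are already in place. The downside is a few more background AEs in both arms. SAP 6.2 describes enrolment in the past tense. If dosing is already complete, the same rules can be applied in a blinded review of phone reports and visit notes before the AE table is produced, although the hold trigger could then no longer act prospectively.

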Sites/ Facilities Enrolling Participants:	
Up to sixteen (16) centers in the United States, that are affiliated with Texan Allergy & Sinus Center will recruit patients. Enrolled subjects will receive treatment at one of three (3) TASC ambulatory surgical centers in San Antonio, Dallas, and Austin, Texas.

Study IRB of Record	
IntegReview IRB [name]
 
IRB Organization (IORG) number: IORG0000689

Description of Study Intervention:	
After informed consent subjects will be randomized 1:1 to receive a series of three (3) injections (0.1 mL) of the allergenic extract (Mountain Cedar Pollen, ALK-Abelló, Inc., Port Washington, NY 11050; US

[figure not shown]
	Government License No. 1256) or diluent as placebo control (sterile saline solution containing 0.4% phenol as a preservative; ALK-Abelló, Inc., Port Washington, NY) every four weeks into a superficial inguinal lymph node through guidance via ultrasonography using a 1-mL hypodermic syringe with a 25-gauge or smaller needle.
Study Duration:	The treatment period will be up to three (3) months, followed by three (3) months of follow-up beginning prior to the start of the 2018-2019 Texas Mountain Cedar allergy season and concluding at the end of the season. The total study duration will therefore be from approximately September 2018 thru August 2019 for completion of data analysis. Study results will be reported within 12 months of study completion.
Participant Duration:	Patients will receive a series of three ILIT injections four weeks apart prior to the start of the 2018-2019 Texas Mountain Cedar allergy season and will be followed monthly for up to four months. The end-of-study visit will be scheduled to take place after the pollen season has ended, as determined by the daily pollen count measures recorded at each participating center. The total study duration for individual participants will be less than seven months.

a Patients that are hypersensitive to Mountain Cedar allergenic extract as defined in section 5.2 (a wheal for allergenic extract greater than that for the positive control), the initial during skin testing are clinically the most likely to benefit from AIT and will therefore be allowed to enroll. Starting doses for these patients are reduced in accordance with section 6.2.

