The investigator or designee will record all events, defined as serious, unexpected, and related adverse drug reactions with start dates occurring any time after the initiation of treatment until seven (7) days after the third treatment will be reported in accordance with the requirements of 21 CFR 312, if applicable, to the manufacturer using their post-marketing safety report system, and to the IRB as an Unanticipated Problem in accordance with Section 8.4. At each study visit, the investigator will inquire about the occurrence of AE/SAEs since the last visit. Unresolved adverse events will be followed for outcome information until the end of the study.

---

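### Protocol 8.3.1 can be read as limiting adverse events to onset within seven days of an injection, which conflicts with the sections that collect them throughout the study

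*Protocol*

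**What the plan says.** Protocol 8.3.1 gives the only general definition of an AE in either document. Onset must follow enrolment and the initiation of treatment, and the latter is "defined as the injection of study treatment and the seven day period following".

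Other protocol sections set no seven-day limit:

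- **8.3.4** says "All AEs occurring while on study must be documented appropriately, according to the definitions in Section 8". It expects events to come to light during both treatment and follow-up, has the investigator ask at each visit about the interval since the last one, and adds that "if the study participant's pre-existing condition deteriorates at any time during the study, it will be recorded as an AE".
- **7.1** treats a new clinically relevant finding after enrolment as an AE and gives no end date.
- **8.1.1.6** and the **1.3 Schedule of Events** include AE review at the end-of-study visit in March to April 2019. The schedule also marks AE review at screening.
- **5.3** keeps serious-event information for screen failures, who are never injected.

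A further window in 8.3.4 applies to serious, unexpected and related reactions "occurring any time after the initiation of treatment until seven (7) days after the third treatment", for onward reporting to the regulator, manufacturer and IRB.

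Protocol 8.3.2 defines a serious event as an AE with certain outcomes. SAP 10.2 summarises the spontaneously reported AEs in the CRF by body system and group. It gives no onset window, and the SAP has no AE definition of its own.

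**The concern.** Staff who follow 8.3.1 literally and staff who follow 8.3.4 or 8.1.1.6 could classify the same event differently, and each could cite the protocol. Take an event that starts two weeks after the first injection, or in January during the pollen season. The end-of-study visit asks about it, but on the narrow reading it is not an AE. Since serious events are a subset of AEs, it could not be a serious AE either.

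The broad sentence in 8.3.4 does not clearly settle this, because it makes documentation depend on the Section 8 definitions, and these include 8.3.1. What reaches the CRF decides what SAP 10.2 can tabulate, so inconsistent recording carries straight into the AE summary. This matters because Protocol 2.2 calls this the first intralymphatic trial for this allergen, and Protocol 2.3.1 says the long-term risks of the route are unknown.

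**Working it through.** The documents state no figure for AE coverage, so there is none to reproduce. The check has two parts: a count of days under each reading, and a comparison of the sections.

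**Inputs**

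- Window per injection: the injection day plus seven days = 8 calendar days (8.3.1).
- Injections: "Patients will receive a series of three ILIT injections four weeks apart" (Synopsis), scheduled on Day 1, Day 28 ± 3 and Day 56 ± 6 (Protocol 1.3, SAP 7.3).
- Time on study: "The treatment period will be up to three (3) months, followed by three (3) months of follow-up" (Synopsis), taken as 6 x 30 = 180 days. "The total study duration for individual participants will be less than seven months" (Synopsis) gives an outer limit of 7 x 30 = 210 days. The 30-day month is my assumption.

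**Reading A: seven days after each injection**

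- Days inside: 1–8, 28–35 and 56–63, so 3 x 8 = 24.
- Share of time on study: 24/180 = 13.3%; 24/210 = 11.4%.
- Share of the treatment span from Day 1 to Day 63: 24/63 = 38%.
- Days outside: 9–27 (19 days), 36–55 (20 days) and Day 64 onward (180 − 63 = 117 days, or 210 − 63 = 147 days). The totals are 19 + 20 + 117 = 156 = 180 − 24, and 19 + 20 + 147 = 186 = 210 − 24.

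**Reading B: continuous from first injection to seven days after the third**

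- Days inside: 56 + 7 = 63. With the visit windows, 50 + 7 = 57 to 62 + 7 = 69.
- Share of time on study at 63 days: 63/180 = 35.0%; 63/210 = 30.0%.
- Across the visit windows: from 57/210 = 27.1% to 69/180 = 38.3%.

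**Reading C: the phrase only marks when treatment begins**

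- There is no end date, so all time after the start is covered.

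Readings A and B both leave most of the time on study outside, including essentially all of the diary period (about December to March). Reading C leaves none outside.

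**Sections side by side**

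| Event | 8.3.1, Reading A | Other sections |
|---|---|---|
| Non-serious event, first onset Day 15 | Not an AE | Asked about at the next visit; to be documented (8.3.4) |
| Serious, unexpected, related reaction, onset Day 15 | Not an AE | Inside the 8.3.4 reporting window |
| Local reaction that starts on Day 3 and persists | AE | Followed to resolution or end of study (8.3.4) |
| New finding in January | Not an AE | AE (7.1); asked about at the end-of-study visit (8.1.1.6) |
| Systemic reaction within 60 minutes | Inside the window | Scored on the Total Safety Score |

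Rows 1, 2 and 4 conflict. Rows 3 and 5 do not.

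**The case against.** The strongest reply is that 8.3.1 does not say what the narrow reading needs. It never refers to each injection. Grammatically the seven-day phrase describes the initiation of treatment, and onset has only to come after that. On this view it sets a start and no end. This stands as a possible reading, so the 24 days and 11–13% are conditional on Reading A. It does not remove the problem, because one sentence that allows three readings cannot serve as the AE definition.

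Several stronger inferences are tempting, and the documents do not support them:

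- **That the safety tables apply the 8.3.1 limit.** SAP 10.2 tabulates what is in the CRF and does not cite 8.3.1. The link is indirect: 8.3.4 ties documentation to the Section 8 definitions, and that governs what is entered. Section 8 also contains 8.3.4 itself, with its whole-study scope, so the deferral does not lead only to 8.3.1.
- **That the first safety objective is undermined.** The composite of anaphylaxis, epinephrine use or another serious treatment-emergent event is limited to 60 minutes after the procedure, as is the Total Safety Score objective. Neither changes under any reading.
- **That 8.3.4 contains a competing AE definition for serious reactions.** That window is for reporting and can legitimately differ from a collection window. It also runs through the gaps between injections.
- **That persistent nodal reactions would be lost.** One that starts within seven days is an AE and is followed up. Only late onset is exposed.
- **That the share of days estimates the share of events lost.** Protocol 2.3.1 says most severe systemic reactions begin within 30 minutes, so treatment reactions should cluster inside every window.

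It is also fair that investigators who follow the visit instructions would record late events. Planned exclusion is not shown; a risk of inconsistent recording is.

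**Conclusion.** The inconsistency is real and worth correcting. Protocol 8.3.1 can be read as limiting AEs to onset within seven days of an injection, and that reading contradicts 7.1, 8.1.1.6 and 8.3.4. On the per-injection reading the definition covers 24 days, about 11–13% of 180–210 days on study. The continuous reading covers about 27–38% once visit windows are allowed for. If the phrase only marks the start of treatment, there is no gap. These are shares of calendar time, with 30-day months assumed.

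What is exposed is narrow: the general AE summary in SAP 10.2, and serious events after the first hour that do not qualify as both unexpected and related, or that start more than seven days after the third injection. The documents do not show that any event was lost.

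**What to change.** 1. In Protocol 8.3.1, remove the seven-day limit from the AE definition. State one collection window, in the same words in 8.3.1 and 8.3.4, that runs through the end-of-study visit.
2. Reconcile the start of that window with AE review at screening (1.3), serious-event information for screen failures (5.3) and findings after enrolment (7.1). Starting at the first injection without further comment would leave those sections in conflict.
3. Keep onset within 60 minutes and onset within seven days of an injection as analysis flags. The separate reporting window in 8.3.4 can stay if it is labelled as such.
4. In SAP 10.2, state that all CRF-recorded AEs are tabulated by group whatever their onset, with those two flags.

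The cost is some wording in both documents and a few more events to record at visits where AE review is already scheduled. SAP 6.2 describes enrolment in the past tense, so the SAP sentence should be settled before unblinding. It cannot recover events that were never entered in the CRF.
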